11.1.2 AE Relationship to Study Drug

The relationship of an AE to the study drug should be assessed using the following the guidelines in Table 2.

Table 2. AE Relationship to Study Drug

Relationship to Drug	Comment
Definitely	Previously known toxicity of agent; or an event that follows a reasonable temporal sequence from administration of the drug; that follows a known or expected response pattern to the suspected drug; that is confirmed by stopping or reducing the dosage of the drug; and that is not explained by any other reasonable hypothesis.
Probably	An event that follows a reasonable temporal sequence from administration of the drug; that follows a known or expected response pattern to the suspected drug; that is confirmed by stopping or reducing the dosage of the drug; and that is unlikely to be explained by the known characteristics of the subject's clinical state or by other interventions.
Possibly	An event that follows a reasonable temporal sequence from administration of the drug; that follows a known or expected response pattern to that suspected drug; but that could readily have been produced by a number of other factors.

Unrelated	An event that can be determined with certainty to have no relationship to the study drug.
-----------	---

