4 STUDY DESIGN

4.1 Study Overview

This is a single center, double-blind, placebo-controlled, randomized study. 30 (number) of subjects are planned. Because the study only investigating the acute effect of the study interventional product, each subject will be administered a single dose of either study dietary supplement or placebo only one time. Subjects will be assigned to the treatments in random order. Evaluations will be taken at baseline and every 30 min following the ingestion of carbohydrates for the following 2 hours at the interval of 30, 60, 90, 120 min.

Screening data will be reviewed to determine subject eligibility. Subjects who meet all inclusion criteria and none of the exclusion criteria will be entered into the study.

The following treatment regimens will be used:

- A dietary supplement E.cava extracted capsule (seaweed) - at dose of 580 mg.
- Placebo (dextrin) – at a dose of 500 mg.

Total duration of subject participation will be six weeks. Total duration of the study is expected to be 12 weeks.

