8.4.1 Dosage/Dosage Regimen

The study test is a dietary supplement called brown seaweed (*Ecklonia cava*) which will be given at 580 mg dose. Seaweed will be administered only one time at the only one visit to investigate the acute effect of the investigational product. administration will be orally.

The placebo is a plain dextrin will be given at 500 mg dose. Placebo will be administered only one time at the only one visit to investigate the acute effect of the investigational product. administration will be orally.

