8.4.3 Administration Instructions

The study dietary supplement (seaweed) or placebo will be administered to patient at the study site only one time at a supervision of study investigator and medical monitor where the patient will be instructed to administer the study capsules orally.

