14.4 Analysis of Secondary Endpoints

Mann-Whitney test will be used to determine differences for symptoms of intolerance between groups.

Adverse events will be tabulated by treatment group and will include the number of patients for whom the event occurred, the rate of occurrence, and the severity and relationship to study drug.

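### The causality table makes dechallenge a condition of 'Probably', which cannot be met when each subject is dosed only once

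*Combined protocol and SAP*

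**What the plan says.** Section 4.1 states that "each subject will be administered a single dose of either study dietary supplement or placebo only one time", and 8.4.1 repeats for the active arm that "Seaweed will be administered only one time at the only one visit", with matching text for placebo. Section 8.4.3 has the product taken on site under supervision.

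Section 11.1.2 directs that relationship to study drug be assessed with Table 2, which has four categories:

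- *Definitely* has two routes, joined by 'or': "Previously known toxicity of agent; or an event that follows a reasonable temporal sequence from administration of the drug". The second route goes on to require a recognised response pattern, dechallenge (an event "that is confirmed by stopping or reducing the dosage of the drug"), and no other reasonable explanation.
- *Probably* has one route. It lists timing and pattern, and then requires that the event be "confirmed by stopping or reducing the dosage of the drug; and that is unlikely to be explained" by the subject's clinical state or other interventions.
- *Possibly* needs timing and pattern, "but that could readily have been produced by a number of other factors". It does not mention dechallenge.
- *Unrelated* needs certainty that there is no relationship.

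There is no row for events where dechallenge does not apply or relationship cannot be assessed. Sections 9.1.6 and 11.1 require relationship to be recorded for adverse events. Section 14.4 tabulates them by treatment group, including "the rate of occurrence, and the severity and relationship to study drug".

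**The concern.** The table is written for repeated dosing, where an assessor can see whether an event subsides once exposure is cut. In this trial exposure is complete when the dose is swallowed. Section 8.7 already recognises what one supervised administration implies, since it declares compliance measurement not applicable for that reason. Table 2 did not receive the same adaptation.

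Safety against placebo is the secondary objective (3.2). If the *Probably* row of the relationship table is empty by construction, a reader of the report may take it as reassurance about the extract. Assessors faced with an event that meets no definition will also have to choose a label by some convention that the protocol does not state, and different assessors may choose differently.

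**Working it through.** No sample size, power or rate enters this point, so the check is one of logic. The plan gives no figure to reproduce.

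**Inputs** (all from Table 2 except D):

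- K: the event is an already known toxicity (yes/no)
- T: timing after the dose is reasonable (set to yes)
- P: the event follows a recognised or anticipated response pattern (yes/no)
- D: dechallenge is possible and confirms the event (no, from 4.1 and 8.4.1; then yes, for comparison)
- A: an alternative explanation is absent, unlikely, or readily available
- U: certainly unrelated (set to no)

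**Rules as written:**

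- *Definitely* = K, or (T and P and D and A absent)
- *Probably* = T and P and D and (A absent or unlikely)
- *Possibly* = T and P and A readily available
- *Unrelated* = U

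With T and U fixed, K, P and A give 2 × 2 × 3 = 12 combinations. More than one category can apply to a combination.

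| Category met | D = no (this trial) | D = yes (repeated dosing) |
|---|---|---|
| *Definitely* | 6 of 12 | 7 of 12 |
| *Probably* | 0 of 12 | 4 of 12 |
| *Possibly* | 2 of 12 | 2 of 12 |
| None | 5 of 12 | 3 of 12 |

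**Reading the table:**

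1. With one dose, *Probably* is never reached.
2. All 6 combinations that reach *Definitely* are those with K = yes. Its second route is closed.
3. Dechallenge accounts for 5 − 3 = 2 of the unclassified combinations: K = no, P = yes, with A absent or unlikely. With dechallenge available, the first meets *Definitely* and *Probably*, and the second meets *Probably*.
4. The other 3 unclassified combinations have K = no and P = no. They fail on the response-pattern clause, with or without dechallenge.

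These are counts of logical combinations. They are not expected frequencies of events.

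**The case against.** **Table 2 is only guidance.** An assessor could treat resolution after the one dose as equivalent to stopping. The protocol does not say so, and any transient symptom in either arm would then satisfy the clause, so it would separate nothing. No other causality rule is given. What stands is that *Probably* is unreachable on the literal text, and an assessor may in practice use it anyway.

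**A reader might infer that every clearly suspected event is unclassifiable, or that both upper categories are closed.** The documents do not support that. The known-toxicity route to *Definitely* needs no dechallenge. It has little documented content: 1.2 reports no significant adverse-effect difference from placebo in earlier studies, and 5.3 names headache, bloating and minor abdominal pain only as example events. But absence of a significant difference does not show that no toxicity is known, and 11.1 refers to an Investigator's Brochure that is not among these documents.

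**A reader might take bloating or headache soon after dosing as the typical unclassifiable event.** That is also too strong. At Visit 2 subjects have a fasting baseline, a carbohydrate load and blood drawn at baseline and at 30, 60, 90 and 120 minutes (10.2, Appendix 1). These would often supply the ready alternatives that make *Possibly* fit. The gap concerns events without such an explanation.

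**A reader might speak of a single capsule.** The text supports only a single dose; 8.4.3 uses the plural: "patient will be instructed to administer the study capsules orally".

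**The consequence is small.** This stands. The between-group safety test is a Mann-Whitney test on symptom scores. Counts and rates by arm do not use the relationship label. Serious events are documented and reported irrespective of cause (11.2.1, 16.2).

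**Conclusion.** The point holds, as a minor inconsistency. Table 2 and the single-dose design cannot both be applied as written: *Probably* is unavailable for all 30 planned subjects, and *Definitely* is available only for a toxicity already known. A suspected event outside that route, with no ready alternative cause, has no category. An empty *Probably* row in the 14.4 tabulation would therefore carry no information about the product.

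The conclusion assumes that Table 2 is applied literally, that the 'or' in *Definitely* marks a separate route, and that no unseen instruction explains how dechallenge is judged after one dose. It does not extend to the safety comparison with placebo, which rests on event counts and symptom scores by randomised arm, nor to the efficacy analysis or sample size.

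**What to change.** Reconcile Table 2 with the single-dose design before any event is classified:

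- Remove the dechallenge clause from *Definitely* and *Probably*, or state how it is met after one dose.
- Separate the categories by onset after the dose, a course consistent with one exposure, and the likelihood of alternative causes such as the carbohydrate load or blood sampling.
- Make sure an event without a recognised response pattern can be classified. Removing the dechallenge clause alone would leave those 3 combinations without a category.
- State which category prevails when two apply. At present a known toxicity with a ready alternative explanation and a recognised pattern meets both *Definitely* and *Possibly*.

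No change to blinding is needed: 8.1 and 8.2 already keep the assessing investigators unaware of assignment until the analysis is complete, apart from emergency unblinding.

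The cost is a wording change in Table 2 and the CRF instructions. The small downside is that causality rests on judgement without dechallenge, which the design already imposes.

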11.2 Serious Adverse Experiences (SAE)

An SAE is defined as any AE occurring at any dose that results in any of the following outcomes:

- death
- a life-threatening adverse experience
- inpatient hospitalization or prolongation of existing hospitalization
- a persistent or significant disability/incapacity
- a congenital anomaly/birth defect

Other important medical events may also be considered an SAE when, based on appropriate medical judgment, they jeopardize the subject or require intervention to prevent one of the outcomes listed.

11.2.1 Serious Adverse Experience Reporting

Study sites will document all SAEs that occur (whether or not related to study drug) per [UCSF CHR Guidelines](#). The collection period for all SAEs will begin after informed consent is obtained and end after procedures for the final study visit have been completed.

In accordance with the standard operating procedures and policies of the local Institutional Review Board (IRB)/Independent Ethics Committee (IEC), the site investigator will report SAEs to the IRB/IEC.

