CONTROL PRODUCT, DOSE AND ROUTE OF ADMINISTRATION	Product plain dextrin as a placebo at 500 mg dose Product will be administered only one time at the only one visit to investigate the acute effect of the investigational product. administration will be orally.
DURATION OF SUBJECT PARTICIPATION AND DURATION OF STUDY	Subjects will be on study for only one time for only 3 hours Screening: one visit Treatment: one time at the only one visit. Follow-up: one day The total duration of the study is expected to be 4 months. 2 months for subject recruitment and 2 months for final subject follow-up as they will visit in different days.
CONCOMITANT MEDICATIONS	
 Allowed: 
 any medication that are not listed in prohibited list. Prohibited: 
 any treatment with either insulin or anti-diabetic drugs. any other natural health products known to impact blood sugar, or polyphenol absorption (e.g. fish oil). Any liver, thyroid, or gastrointestinal disorders medications.
EFFICACY EVALUATIONS	NA
PRIMARY ENDPOINT	
 Plasma glucose concentration will be determined immediately by blood finger-prick sample following standard procedure using Accu-Chek® aviva (Roche Diagnostics, Rotkreuz, Switzerland), Whereas, plasma insulin will be measured at the laboratory department at KKUH using enzyme-linked immunosorbent assay (ELISA)
SECONDARY ENDPOINTS	
 Participant/s will be asked to indicate whether side effects are absent, mild, moderate or severe by giving scores as 0,1,2,3, respectively. The side effect questionnaire, will be required to be completed within 24 hours after intervention or placebo ingestion.
OTHER EVALUATIONS	NA
SAFETY	Change in blood glucose level from baseline to more than 240 mg /dl or

EVALUATIONS
	
less than 70 mg /dl Adverse events such as: Headach, Bloating or Minor abdominal pain

PLANNED INTERIM ANALYSES
	
When approximately 50% of patients have completed the study through Visit 2, an interim analysis for safety will be conducted by an independent data monitoring committee. Serious adverse events will be monitored by the committee on an ongoing basis throughout the study.

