5.2 Secondary Efficacy Endpoints

In order to assess side effects of study intervention, measurement of side effects will be obtained by using an arbitrary scale, similar to that used by Paradis et al (12), that allow participants to rate symptoms of intolerance by indicating whether each side effect was absent (0), of mild intensity (1), of moderate intensity (2), or of severe intensity (3). The side effect questionnaire, will be required to be completed within 24 hours after intervention or placebo ingestion. The side effect will include headache, energy levels, appetite, gastrointestinal symptoms, unusual pain or sensations, cardiac palpitations, balance disorders, and anxiety.

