10 EVALUATIONS BY VISIT

10.1 Visit 1 (Day1 /Week 1/Month 1)

1. Review the study with the subject (subject's legal representative) and obtain written informed consent.
2. Assign the subject a unique screening number.
3. Record demographics data.
4. Record medical history, including a history of pre-diabetic, diagnosis date.
5. Perform a complete physical examination.
6. Perform and record vital signs.
7. Perform and record results of blood pressure testing.
8. Collect blood for clinical laboratory tests (baseline of blood glucose level).
9. Schedule subject for Visit 2 in different days.
10. List all additional procedures, such as Randomize subject

10.2 Visit 2

1. Perform abbreviated physical examination.
2. Perform and record vital signs.
3. Collect blood for clinical laboratory tests (baseline of blood glucose and insulin levels).
4. Administer either study dietary supplement (seaweed) or placebo based on blinded randomization.
5. Perform carbohydrates ingestion
6. Collect blood for clinical laboratory tests (blood glucose and insulin levels 30 min after administration of study treatment).
7. Collect blood for clinical laboratory tests (blood glucose and insulin levels 60 min after administration of study treatment).
8. Collect blood for clinical laboratory tests (blood glucose and insulin levels 90 min after administration of study treatment).
9. Collect blood for clinical laboratory tests (blood glucose and insulin levels 120 min after administration of study treatment).

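### SAE collection closes with Visit 2, on the listed procedures about 2 to 3 hours after dosing, although the protocol names one day of follow-up and a 24-hour side-effect form that no scheduled step collects

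*Combined protocol and SAP*

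**What the plan says.** **SAE period.** Section 11.2.1 opens collection of all SAEs once consent is given and has it "end after procedures for the final study visit have been completed". No hour is given.

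**Final visit.** Sections 10.1 and 10.2 and Appendix 1 define two scheduled visits; Section 10.3 adds one for early withdrawal. The last of the nine numbered steps in Section 10.2 is a draw for "blood glucose and insulin levels 120 min after administration of study treatment". Section 4.1 starts the clock at the meal instead: "every 30 min following the ingestion of carbohydrates for the following 2 hours at the interval of 30, 60, 90, 120 min". The synopsis, under duration of participation, says "Subjects will be on study for only one time for only 3 hours".

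**Period after the visit.** The same synopsis entry says "Follow-up: one day". Section 5.2 makes a self-rated side-effect questionnaire the secondary endpoint, and it "will be required to be completed within 24 hours after intervention or placebo ingestion". Section 14.4 compares symptom scores between groups with a Mann-Whitney test.

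**AE enquiry.** Section 11.1 has the investigator ask about AEs at subject visits. Section 9.1.6 says AEs are captured for the duration of the study, without saying when that ends for a subject. Section 4.1 gives participation as six weeks.

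**Schedule.** Neither Section 10.2 nor Appendix 1 contains the questionnaire, its return, or a call or visit after Visit 2.

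**The concern.** The protocol treats the day after a single dose as a period in which reactions matter: it names a one-day follow-up and allows a side-effect form up to 24 hours. Its SAE rule is tied to a visit whose listed procedures finish within the first few hours, and nothing in the schedule carries out the follow-up.

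Two things are at stake. The first is safety capture. A serious event on the evening after dosing would fall outside the stated SAE period on the listed procedures, and no planned contact would bring it to light. The independent committee's ongoing SAE review and its safety look at about 50% of patients (Section 14.5) can use only what is collected.

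The second is the secondary endpoint. Safety is the sole secondary objective (Section 3.2) and the questionnaire is its endpoint. A completion deadline does not define an observation period, so two participants can each comply while reporting on very different lengths of time.

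**Working it through.** The plan gives no figure to reproduce here. The check compares time windows.

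**Inputs**
- Questionnaire window: up to 24 h after ingestion (Section 5.2 and synopsis). This matches the one-day follow-up in the synopsis.
- End of Visit 2 procedures, lower value: 2 h after dosing (120-minute sample, Section 10.2).
- End of Visit 2 procedures, upper value: 3 h (session length in the synopsis), assuming that the session does not begin after dosing.
- Section 4.1 times the same samples from the carbohydrate load. The gap between capsule and load is not stated, so on that clock the last sample falls at 2 h plus the gap. A gap of 0.5 h is used below purely as an illustration.

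**Share of the 24 hours after the SAE cut-off** = (24 − end of procedures) / 24

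| Basis for the end of procedures | End (h) | Hours after cut-off | Share |
|---|---|---|---|
| Section 10.2 | 2 | 24 − 2 = 22 | 22/24 = 0.917 (92%) |
| Section 4.1 with an assumed 0.5 h gap | 2.5 | 24 − 2.5 = 21.5 | 21.5/24 = 0.896 (90%) |
| Synopsis session length | 3 | 24 − 3 = 21 | 21/24 = 0.875 (88%) |

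**If the questionnaire is taken as a Visit 2 procedure.** The SAE period would then run until the form is completed. The end would differ by subject, from the end of sampling (2 to 3 h) for an early form to 24 h for a late one. The rule would still not guarantee one day.

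**Period covered by the form.** A form completed at 1 h covers 1/24 = 4% of the window. One completed at 23 h covers 23/24 = 96%. Both meet the deadline.

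**Whether another provision fills the gap**
- Section 11.1 ties AE enquiry to visits, and no visit follows Visit 2.
- The early withdrawal visit (Section 10.3) and follow-up of an AE until it resolves or stabilises (Section 12.1) do not reach a subject who completes normally.
- The AE row in Appendix 1 has one mark, which reads as Visit 2, and the table has no later column.
- Section 9.1.6 depends on when the study ends for a subject. The documents give 3 hours, one day and six weeks.

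**The case against.** The strongest reply is that the cut-off of 2 to 3 hours is inferred. Section 11.2.1 states no hour, and the list in Section 10.2 is not exhaustive: Appendix 1 shows height and weight at Visit 2, and apparently also AE and concomitant-medication review, none of which Section 10.2 mentions. A required questionnaire could likewise be an unlisted part of Visit 2, and SAE collection would then run until it is completed. This stands as a limit on certainty. It does not remove the problem, because neither place says so and the SAE end-point would then depend on when each person filled in a form.

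A reader might infer that a serious event that evening would go unreported. The documents do not support that. Section 9.1.6 calls for AE capture during the study, Section 14.5 for ongoing SAE monitoring, Section 16.2 for SAEs to go to the ethics committee whatever their cause, and Section 16.5 for AEs and unanticipated problems to be reported. An event that came to light could be reported under these. What they lack is a scheduled contact and a clear end of collection. Section 11.3 on medical monitoring is listed in the contents but is not in the text available, so nothing is claimed about it.

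A reader might also infer that the variable form timing biases the treatment comparison. That is not shown: the deadline is the same in both arms and Section 8.2 blinds participants and staff. Nor are late symptoms necessarily lost; that can happen only on forms completed early.

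The low expected risk of a single supplement dose bears on how serious the gap is, but does not reconcile the sections.

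**Conclusion.** The point holds as an internal conflict with a practical consequence. On the listed procedures, SAE collection closes about 2 to 3 hours after dosing, leaving 21 to 22 of the 24 hours (88% to 92%) of the protocol's own follow-up outside it. No contact after Visit 2 appears in Section 10 or Appendix 1 for subjects who complete, and the wording applies to all 30 planned.

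This rests on two assumptions: that the listed Visit 2 steps mark the end of final-visit procedures, and that the 24-hour deadline together with the one-day follow-up indicates the period that the protocol means to cover. The percentage describes a time window, not the number or probability of events missed.

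For the secondary endpoint, the consequence is unequal observation periods, hence noise and possible under-ascertainment in a small trial. The plan should be changed before dosing, since events not asked about at the time may not be recoverable later.

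**What to change.** 1. Reconcile the duration entry in the synopsis and Sections 4.1, 5.2, 9.1.6, 10.2, 11.2.1 and Appendix 1 on when participation and AE/SAE collection end for a subject.
2. In Section 11.2.1, end AE and SAE collection no earlier than the 24-hour follow-up that the protocol already names.
3. In Section 10.2 and Appendix 1, add the side-effect questionnaire as a scheduled item, completed at 24 hours for the whole 0 to 24 h period. Record AEs and SAEs when the form is returned or in a short call.
4. In Section 5.2, replace the completion deadline with that fixed recall period, so that every form covers the same time.

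The cost is about 30 short contacts, one per participant, plus the wording changes. Blood sampling, dosing and the primary analysis are untouched.
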